7.1.1 Index procedure

1. After angiographically successful PCI of the CTO target vessel (no remaining lesion proximal or in-stent $\geq 30\%$, confirmed in two orthogonal projections with an angle ≥ 25 degrees apart), physiologic measurements must be performed in this vessel before additional OCT.

2. Physiologic assessment
 - Physiologic measurements must be performed using the Coroflow system (Coroventis) in combination with the PressureWire X (Abbott).
 - Physiologic measurements must be performed using intravenous adenosine and in the following order:
 - 1) Ensure adequate guide catheter position and adequate proximal venous access
 - 2) Administration of intracoronary nitrate (100 or 200 mcg)
 - 3) **RFR** 10 mm *proximal* to proximal stent edge.
 - 4) **Pd/Pa** (proximal arterial pressure/proximal aortic pressure without adenosine)
 - 5) **RFR** 10 mm *distal* to distal stent edge (without adenosine)
 - 6) **Pd/Pa** (distal arterial pressure/proximal aortic pressure without adenosine)
 - 7) Go to **CFR/IMR** mode: follow the steps and potential troubleshooting steps as indicated by the Coroventis software
 - Obtain the required hyperemia by infusion of intravenous adenosine with a dosage of 140 mcg/kg/min
 - **CFR** and **IMR** are calculated automatically.
 - Maintain hyperemia by continuing the infusion of adenosine
 - 8) Go to **FFR mode**:

- 10 mm *distal* to distal stent edge: FFR measurement after 20 heart beats during stable maximal hyperemia
- 10 mm *proximal* to proximal stent edge: FFR measurement after 20 heart beats during stable maximal hyperemia
- Stop infusion of adenosine
- **Check drift:** if drift >0.03 repeat physiologic measurements (description "drift")
- Additional OCT will be performed during the index procedure or staged when indicated..

3. OCT

- OCT imaging of the stented segment in the CTO target vessel; starting and visualizing 10 mm distal from the stent edge and ending/visualizing 10 mm proximal of the stent edge.
- Based on the OCT findings and/or physiologic assessment, stent optimization (postdilation or additional stent placement) to eliminate treatable components of SSR (as defined in appendix I) is left to the operator's discretion.
- Distal RFR and distal FFR should be repeated after stent optimization
- It must be noted on the designated form which component(s) of SSR were seen and treated by the operator.
- In case the operator decides to perform one or more additional interventions or decides to refrain from additional interventions, it will be noted on the designated form what motivated the operator to do so
- End of procedure.

7.1.2 Staged procedure (within 4 ± 2 weeks)

- 1) OCT may be performed during a staged procedure when indicated (i.e. high contrast use, procedural duration, major dissection or other safety reasons according to the operator). See details for OCT at 7.1.1, section 3.
- 2) For patients with a remaining intermediate stenosis (angiographically 30-90%) in a non-CTO vessel or major side branch of the CTO vessel with diameter $\geq 2\text{mm}$, clinically indicated FFR guided PCI will be planned within 4 ± 2 weeks. During this staged procedure, intra-coronary physiologic assessment (RFR, FFR, CFR and IMR) will be repeated in the CTO vessel for exploratory objectives (before additional PCI).
- 3) When the operator decides to optimize the CTO stent result (post-dilation or additional stenting), post-PCI RFR and FFR should be repeated.

7.2 Data transfer and analysis

All physiologic measurements and OCT recordings at index – and staged procedure for exploratory purposes (see paragraph 7.1.1 and 7.1.2) must be stored and the anonymized raw data must be send to Radboudumc Technology Center. Physiologic data will be checked and analysed by the researchers. The specific OCT analyses will be performed by the researchers.

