6.4 Sample size calculation

This study is aimed at assessing a difference in the AUCs of paired data where each subject (with and without SSR) is subjected to FFR and RFR measurement post-PCI. This procedure compares two ROC curves for the paired sample case where in each subject has a known condition value (SSR) and test values from two diagnostic tests (RFR and FFR). The test values are paired because they are measured on the same subject.

Researchers wish to show that a new classification method works at least as well as the current method. The trial is powered for non-inferiority.

Based on previous studies the area under the curve of FFR in relation to SSR is assumed to be 0.90 and the incidence of SSR is assumed to be 40%^{6, 7, 13}.

Assuming an AUC of 0.90 for FFR, with a significance level α of 5%, and a non-inferiority limit margin 0.10 and an estimated prevalence of SSR of 40%, a total of 190 patients are needed to obtain a power of 80%. To account for a drop out of 5%, the sample size will be increased to 200 patients.

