8.1 Study endpoints

8.1.1 Primary study endpoint

Primary endpoint is defined as:

The AUC of post-PCI RFR compared to the AUC of post-PCI FFR with regard to SSR.

Components of combined endpoint of SSR: Geographical miss (A), stent mal-apposition (B), stent mal-expansion (C) and intra-stent plaque protrusion/thrombus (D), edge dissection (E), as depicted in Figure 1. Definitions are described in appendix I.

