8.2 Randomisation, blinding and treatment allocation

There will be no randomisation and thus no blinding of the randomisation assignment.

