8.3.1 Baseline (pre procedure)

Screening of eligible patients will be performed by the researchers. Eligible patients meeting the inclusion criteria will be asked for informed consent by one of the researchers. The operator will be informed about participation in the trial.

Accordingly the following baseline characteristics will be obtained before start of the procedure: patient characteristics, medical history, risk factors, blood sampling (creatinine clearance), the indication for the CTO PCI and specific characteristics of the CTO.

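### The protocol does not mask whoever scores SSR to RFR, FFR and the operator's form, nor say whose OCT assessment defines SSR for the primary comparison

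*Protocol*

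**What the plan says.** - **Who analyses what.** Section 7.2: "Physiologic data will be checked and analysed by the researchers. The specific OCT analyses will be performed by the researchers". No division of tasks, reading order or masking is given.
- **Order of measurement.** Section 7.1.1: "physiologic measurements must be performed in this vessel before additional OCT". RFR, FFR, CFR and IMR therefore exist before any OCT can be read.
- **Operator's form.** Section 7.1.1, item 3 (OCT): "It must be noted on the designated form which component(s) of SSR were seen and treated by the operator". The same item lets the operator act on OCT, physiology or both, so the person completing the form has the pressure results.
- **Data transfer.** Section 7.2: "the anonymized raw data must be send" to a technology centre.
- **Blinding.** Section 8.2, the only text on the subject: "There will be no randomisation and thus no blinding of the randomisation assignment".
- **Endpoint.** Section 8.1.1 compares the two AUCs for SSR and lists its parts: "Components of combined endpoint of SSR: Geographical miss (A") and four others, with definitions in Appendix I. Neither place names whose assessment counts.
- **Further detail.** Section 7.1 refers to a Standard Operating Procedure (SOP) for the study-related measurements at the procedures. Section 10 refers to a separate SAP. Neither is shown.

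**The concern.** In a comparison of two diagnostic indices, the reference standard should be set without knowledge of either. If a reader who knows an index lets it tip borderline SSR calls, SSR partly contains that index and the index's AUC is inflated. The non-inferiority decision rests on the difference between two AUCs, so a shift in one of them, or unequal shifts in both, moves the primary result.

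This cannot be left to the analysis stage. Once labels have been assigned with the pressure results in view, no statistical method applied to them recovers the masked labels. Only a fresh masked reading of the stored recordings would.

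**Working it through.** **1. The plan's own figure.** Section 6.4 gives 190 evaluable patients: AUC 0.90, SSR 40%, margin 0.10, α 5%, power 80%. Section 10.2 makes the test one-sided through a 90% interval. The correlation between the AUC estimates is not stated; I assume 0.
- Requirement: 0.10 / √(2·Var) ≥ z(0.95) + z(0.80) = 1.645 + 0.842 = 2.486.
- Obuchowski binormal variance: Var = 0.0099·exp(−a²/2)·[(5a² + 8) + (a² + 8)/k] / n₁, with a = 1.414 × 1.2816 = 1.812 and k = 60/40 = 1.5. This gives Var ≈ 0.0612/n₁.
- Then n₁ ≥ 2 × 0.0612 × 2.486² / 0.01 ≈ 75.7, so 76 SSR patients and N = 189, against the stated 190. With 5% dropout, 190/0.95 = 200.

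The sample size is reproduced, and masking would not change it. The point rests on no figure in the plan.

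**2. What each passage does for masking.**

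| Place | What it settles | Does it mask the SSR assessor? |
|---|---|---|
| 7.2, analysis | The researchers handle both data types | No |
| 7.2, transfer | Patient identity removed | No; RFR and FFR are not identity |
| 7.1.1, order | Physiology precedes OCT | No; it makes the values available |
| 7.1.1, item 3 | The operator records SSR components | No; the operator knows the physiology |
| 8.2 | Randomisation assignment | No |
| Appendix I | Numeric criteria for each component | No; it narrows judgement |

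The statistics chapter and the monitoring section (12.2) do not mention masking either.

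**3. Patients exposed.** Section 6.4 states that "the incidence of SSR is assumed to be 40"%. With 190 patients, 0.40 × 190 = 76 have SSR and 0.60 × 190 = 114 do not. If any single component makes SSR positive, which 8.1.1 suggests by calling it combined but does not spell out, one swayed positive call would change the label of any of the 114. A swayed negative call would change one of the 76 only where that component stands alone.

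**4. Illustration of size.** Everything here except the 40% SSR, the AUC of 0.90 for FFR and the margin is assumed. A label that follows an index becomes positive when that index lies in its worst 40%.

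*Both true AUCs 0.90, within-group correlation about 0.6, 10/20/30% of labels following one index:*
- Random labels: about 3/7/10 of 190 labels change, and the difference shifts by about 0.01/0.02/0.03.
- Only the labels nearest the SSR threshold: about 9/16/22 change, and the shift is about 0.02/0.05/0.07.
- The sign depends on which index leads. If both lead (random labels), the difference stays near 0 while each AUC rises to 0.907/0.914/0.922.
- Sensitivity to correlation: about 0.003 at 0.9 (random labels, 10%), and up to 0.094 at about 0.4 (borderline labels, 30%).

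*True AUCs 0.90 (FFR) and 0.80 (RFR), so the true difference of -0.100 lies on the margin; correlation 0.6, random labels:*
- Following RFR in 5/10/20%: -0.087/-0.075/-0.052.
- Following FFR in 5/10/20%: -0.102/-0.104/-0.108.
- Following both in 20%: about -0.083.

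The last case bears most on a false claim of non-inferiority, because a reader who sees one index probably sees the other.

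**The case against.** The strongest reply is that this is silence, not a stated error. Section 7.2 does not prescribe an unmasked reading, and the SOP or SAP may contain a masking rule. That limits the wording: the point is that masking is not specified. It does not remove the point. What an SSR assessor may see is a matter of study conduct, and 7.2 settles who reads while leaving open what they may know.

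A reader might infer that the same people read both data types. The documents do not support this. The researchers is a loose term: 8.3.1 says "Screening of eligible patients will be performed by the researchers" and has one of them ask for consent, while 11.2 gives consent to one of the cardiologists. The shared term neither shows nor excludes shared readers.

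A reader might also infer that the researchers' OCT reading is stated to define SSR. It is the natural reading, but no section says so. If the operator's form were used instead, the assessor would certainly know the pressure results.

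Reader discretion is limited. Appendix I gives a numeric criterion for every component (for example, malapposition needs at least 200 µm in at least 5 consecutive frames), and 7.1.1 fixes the imaged window at 10 mm beyond each stent edge. This stands in part. Contour tracing, choice of the reference segment (usually, not always, within 10 mm) and values close to a cut-off still need judgement.

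Finally, recordings are stored, so the gap can be repaired. That is true, and it is why the remedy is cheap.

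**Conclusion.** The point holds in this form: the protocol neither masks the SSR assessor to the physiology results and the operator's form nor says which assessment defines SSR for the primary AUC comparison. An unmasked reading would comply with it and could bias the AUC difference.

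The documents give no size or direction. The shifts above come from an assumed mechanism and are neither estimates nor bounds. They run from about 0, when both indices lead and the AUCs are equal, to a substantial part of the 0.10 margin when one index drives borderline calls. It would be wrong to infer that the trial is biased towards non-inferiority, or that bias of any given amount is expected. The conclusion rests on two things only: some SSR calls need judgement, and nothing in the protocol keeps the pressure results from the person making them. The sponsor should settle this before SSR is scored.

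**What to change.** In section 7.2, with a cross-reference in 8.2, state that:
- SSR for the primary analysis is defined by the researchers' reading of coded OCT recordings under Appendix I;
- this reading is done without access to RFR, FFR, CFR, IMR or the operator's form;
- the SSR labels are locked before they are merged with the physiology data.

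If the SOP already provides this, cite it in 7.2. If some recordings have already been read with the physiology in view, a masked re-reading of the stored recordings would restore the reference standard.

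The cost is a small data-handling burden: coding the recordings, splitting tasks or reading under separate codes, and locking the labels. The number of researchers is not stated, so splitting the tasks may need some scheduling. No additional reader, procedure or patient is needed, the sample size is unchanged, and what operators see and decide during the procedure is not affected.

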8. METHODS

[figure not shown]
8.1 Study endpoints

8.1.1 Primary study endpoint

Primary endpoint is defined as:

The AUC of post-PCI RFR compared to the AUC of post-PCI FFR with regard to SSR.

Components of combined endpoint of SSR: Geographical miss (A), stent mal-apposition (B), stent mal-expansion (C) and intra-stent plaque protrusion/thrombus (D), edge dissection (E), as depicted in Figure 1. Definitions are described in appendix I.

8.1.2 Secondary study endpoints (definitions in appendix I)

Secondary endpoints are defined as :

- The predictive value of the RFR and FFR gradient across the stented segment with regard to SSR in CTO patients.
- The correlation between positive RFR (≤ 0.89) and positive FFR (≤ 0.80) with regard to SSR following angiographically satisfactory CTO PCI.
- The correlation between post-PCI physiology (RFR, FFR, CFR, IMR) and SSR with anginal complaints (SAQ score), NYHA and CCS classification and MACE at follow-up.

- The correlation between OCT and/or physiology findings and physician-decision making (perform or refrain from additional PCI)

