5. STUDY DESIGN

ULTRA-CTO is a prospective multicentre non-randomised investigator-initiated trial designed to enrol 200 subjects with an indication for PCI CTO.

After angiographically successful CTO PCI, intra-coronary physiologic assessment (RFR, FFR, CFR and IMR) and subsequent OCT of the CTO vessel will be performed. OCT may also be performed during a staged procedure when indicated (i.e. high contrast use, procedural duration, major dissection or other safety reasons according to the operator)..

[figure not shown]
When intra-coronary physiologic assessment or OCT is not possible at all, the patients will not be included in the study (6.1).

When the operator decides to optimize the stent result (post-dilation or additional stenting), based on the OCT and/or physiology, post-PCI RFR and FFR should be repeated.

For patients with a remaining intermediate stenosis (angiographically 30-90%) in a non-CTO vessel or major side branch of the CTO vessel with diameter ≥ 2 mm, clinically indicated FFR guided PCI will be planned within 4 ± 2 weeks. During this staged procedure, intra-coronary physiologic assessment (RFR, FFR, CFR and IMR) will be repeated in the CTO vessel for exploratory objectives (before additional PCI).

At 4 ± 2 weeks follow-up, the occurrence of cardiovascular events and clinical classification will be assessed for secondary objectives. See figure 2 for the study flow chart. A description of the primary and secondary endpoint(s) is included in paragraph 8.1.

Figure 2. Flowchart ULTRA-CTO

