8.3.1 Staged procedure

At 4 weeks, prior to the staged procedure, clinical classification, occurrence of (S)AEs including MACE and other events will be registered.

Similar to the index procedure, several variables regarding procedure-related technical characteristics and the study-related physiologic measurements will be collected during the staged procedure.

Study procedure	Baseline (pre procedure)	Index procedure / hospitalization	Staged procedure (subset of patients)	Follow-up 4 ± 2 weeks
Patient eligibility: Inclusion/exclusion	X ¹			
Patient informed consent	X ²			
Baseline characteristics: - Patient characteristics - Blood sample (creatinine clearance) - Use of medication - Medical history - Risk factors - Indication for CTO PCI - CTO characteristics	X X ³ X X X X			
PCI procedure variables - Technical characteristics - Physiology parameters - OCT		X X X	(X) (X) (X)	
Clinical classification⁴	X			X
Adverse events and complications		X	(X)	X

Figure 3. Study procedures

1. This study will be conducted in subjects fulfilling all inclusion criteria and none of the exclusion criteria (see paragraph 6.1 and 6.2).
2. Written informed consent will be obtained before enrollment in the trial.
3. Blood sampling (creatinine clearance) will be performed according to standard care. No more than 20 ml of blood will be obtained during each sample.
4. CCS classification, NYHA classification and at staged procedure also SAQ score, TLR, ST, MACE, TVF.

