10.3 Analysis of secondary outcomes

Pearson r correlation and Spearman correlation coefficient rho (r) will be used to evaluate the degree of relationship between variables. For normally distributed variables, we will use the Pearson r correlation, while in case of skewed, ordinal data, the degree of association between variables will be quantified using Spearman correlation coefficient rho (r).

For repeated measurements (RFR, FFR, and other physiological parameters) we will use the paired t test for normally distributed variables and the Wilcoxon signed-rank test for skewed continuous data.

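### The symptom endpoint in 8.1.2 uses follow-up CCS, NYHA and SAQ alone in a plain correlation, although baseline CCS and NYHA are recorded; the timing of the symptom and SAQ assessments also needs reconciling

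*Protocol*

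**What the plan says.** - **Endpoint.** Section 8.1.2 relates CTO-vessel findings to symptoms and MACE, and takes the clinical side at follow-up only: "The correlation between post-PCI physiology (RFR, FFR, CFR, IMR) and SSR with anginal complaints (SAQ score), NYHA and CCS classification and MACE at follow-up".
- **Time.** Section 5: "At 4 ± 2 weeks follow-up, the occurrence of cardiovascular events and clinical classification will be assessed for secondary objectives".
- **Residual disease.** Section 5 also describes a subset: "For patients with a remaining intermediate stenosis (angiographically 30-90%) in a non-CTO vessel or major side branch of the CTO vessel". For them, "clinically indicated FFR guided PCI will be planned within 4 ± 2 weeks", which is the same window as the symptom assessment.
- **Order.** The section on the staged procedure (numbered 8.3.1 in the text, 8.3.4 in the contents) says: "At 4 weeks, prior to the staged procedure, clinical classification, occurrence of (S)AEs including MACE and other events will be registered".
- **Schedule.** In Figure 3 the row "Clinical classification⁴" is marked at baseline and at follow-up. It is not marked in the staged-procedure column. Footnote 4 and Appendix I define this item as CCS and NYHA, and add SAQ only at the staged procedure.
- **Method.** Section 10.3: "Pearson r correlation and Spearman correlation coefficient rho (r) will be used to evaluate the degree of relationship between variables". It gives no role to baseline symptoms or to remaining stenosis. Section 10 leaves further technical detail to a separate SAP.

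**The concern.** Symptoms a few weeks after PCI depend heavily on symptoms before it. A correlation that uses only the follow-up class leaves this between-patient variation in the outcome as noise, although the protocol already collects the baseline class that could remove part of it. A real but weak link between physiology or SSR and symptoms is then easier to miss.

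In addition, patients with a known stenosis elsewhere may have angina that does not come from the CTO vessel. On the text of the staged-procedure section, they are assessed while that stenosis is untreated. The stated analysis gives no view of whether the association depends on them.

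Finally, the schedule does not settle which symptom value counts in staged patients, or who completes the SAQ. SAQ is the angina measure named in 8.1.2.

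**Working it through.** **The plan's own figure.** The protocol computes nothing for this endpoint. Its only computed figure is the primary sample size, which supplies n = 190 below. It reproduces with the Obuchowski binormal variance, AUC 0.90 for both tests, 40% prevalence, one-sided 5%, 80% power and a between-test correlation of 0 (the last is not stated in the protocol). This gives exactly 190, and 190/0.95 = 200.

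**Step 1: the precision lost by ignoring baseline.** Inputs not in the documents are the true correlation r, the baseline-to-follow-up correlation b, and a two-sided 5% test. Baseline is taken as unrelated to physiology and SSR. Fisher's z gives power = Φ(atanh(r)·√(n−3) − 1.96), with √187 = 13.67. After adjustment, r becomes r/√(1−b²).

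| b | variance left, 1−b² | r = 0.15 becomes | power | power if r = 0.20 |
|---|---|---|---|---|
| none | 1 | 0.150 | 54% | 79% |
| 0.3 | 0.91 | 0.157 | 58% | 83% |
| 0.5 | 0.75 | 0.173 | 67% | 90% |
| 0.7 | 0.51 | 0.210 | 83% | 98% |

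For example, at b = 0.5: 0.15/√0.75 = 0.173, atanh = 0.175, 0.175 × 13.67 = 2.39, and Φ(2.39 − 1.96) = 67%. In terms of sample size, 190/(1−b²) is 209, 253 and 373 patients. For ordinal classes the Fisher approximation is rough, so the table shows the order of magnitude.

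**Step 2: what residual disease could do.** All inputs here are assumed.
- *As noise only.* If a share s of patients has symptoms shifted by d SD, a correlation shrinks by 1/√(1+s(1−s)d²). For s from 0.1 to 0.5 and d from 0.3 to 0.8, the factor is 0.996 to 0.93. This is small.
- *As a common cause, for SSR.* If residual disease is q more frequent with SSR (SSR 40%, s = 0.3), the false correlation is q·d·√(0.4·0.6)/√(1+0.21d²). With q = 0.1 and d = 0.5 this is 0.0245/1.026 = 0.02. With q = 0.3 and d = 0.8 it is 0.1176/1.065 = 0.11.
- *As a common cause, for RFR or FFR.* Take 40% with residual disease, 15 SAQ points worse, within-group SD 20. The correlation of residual disease with SAQ is 15·√0.24/√(400+54) = 0.345. If residual disease correlates 0.1 to 0.4 with physiology, the false correlation is 0.03 to 0.14.

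**Step 3: the schedule read side by side.** The text places the assessment before the staged procedure. The grid has no classification mark in the staged column and a separate follow-up column, so it does not show that order. Footnote 4 ties SAQ to the staged procedure, where the grid has no mark, while 8.1.2 wants SAQ at follow-up. No baseline SAQ is scheduled. Read literally, SAQ exists only in staged patients, and that number is not given. The smallest correlation detectable with 80% power, tanh((1.960+0.842)/√(n−3)), is 0.202 at n = 190, 0.277 at 100, 0.355 at 60 and 0.431 at 40.

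**The case against.** The strongest reply is that covariates and subgroup displays belong in the SAP, which is not shown, and that nothing in the protocol forbids them. This stands in part: one can say only that the protocol gives baseline no role, not that baseline will go unused. But the endpoint as a follow-up level and the named correlation methods are set in the protocol, and an SAP that follows them literally would be unadjusted.

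Two stronger readings are tempting, and the documents do not support them.
- A reader might infer that symptoms are measured after other vessels have just been treated. The staged-procedure text says the opposite. Only the layout of the Figure 3 grid leaves that open.
- A reader might infer that residual disease makes the correlation spurious. No section links disease in another vessel to CTO-vessel RFR, FFR or SSR. Section 6.1 excludes a remaining lesion of 30% or more proximal to the stented segment, and section 7.1.1 adds in-stent lesions. The top of the assumed range would matter: at r = 0.11, 0.1104 × 13.67 = 1.51, and the chance of exceeding 1.96 is about 33%. Nothing in the documents places the trial there.

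It is also fair that the protocol promises a correlation, not a causal reading of the CTO stent. That argues against making patients without remaining stenosis the main analysis. Such a restriction would change the estimand, and on the literal SAQ schedule it would leave SAQ only in those staged for OCT.

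**Conclusion.** The point holds as a matter of method and consistency. For CCS and NYHA, adjustment for the recorded baseline class is better than a plain follow-up correlation. Its benefit is mainly precision: power of 58% to 83% instead of 54% for a true correlation of 0.15 with 190 patients, if baseline and follow-up correlate 0.3 to 0.7 and baseline is unrelated to physiology and SSR.

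Confounding by residual disease is plausible but unproven. The illustrative false correlations (0.02 to 0.14) rest wholly on assumed inputs, so this part merits a sensitivity analysis and no more. The conflict over when symptoms and SAQ are recorded is in the text itself and must be resolved, because SAQ could otherwise be missing in most of the intended population. This is one secondary endpoint; the primary AUC comparison is unaffected.

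**What to change.** 1. In 8.1.2 and 10.3, estimate the association of physiology and SSR with follow-up CCS and NYHA adjusted for the baseline class, for example by partial Spearman correlation or ordinal regression. Keep all patients in this main estimate.
2. Add a sensitivity analysis adjusted for, or stratified by, remaining 30-90% stenosis (yes/no). Staged status is not a substitute, because section 7.1.2 also allows staging for OCT alone.
3. State that the symptom value used in staged patients is the one recorded before the staged procedure, as the staged-procedure text says, and align the Figure 3 grid with it.
4. Reconcile footnote 4 and Appendix I with 8.1.2 on who completes the SAQ and when. Without a baseline SAQ, baseline CCS is only a partial covariate for it, and the plan should say so.

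For CCS and NYHA the cost is wording and a little more analysis, since the baseline class is already scheduled. Remaining stenosis must be known to plan the staged procedure, but no section lists it as a recorded variable, so its capture in the eCRF should be confirmed. Extending SAQ to all patients, if that is the intention, would need a data-collection change where it is not already done.
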